#### Protocol

#### Pre tests

Prior to the formal test, the participant will undergo at least two anti-terrorist combat simulations to familiarise him/herself with the process of the formal test. The timer will start when the participant passes through the entrance on the first floor. The test will simulate the daily counter-terrorism duties of special forces personnel, conducting space searches and clearing out enemies. Ten targets are placed in the space to be attacked. When the participant finishes clearing the enemies on the first floor, he/she will enter the ground floor to continue searching and clearing the enemies in the space and return to the entrance of the first floor as soon as possible when he/she touches the simulated hostages. Each enemy will be scored using a 10-point target paper. The task completion time and the total score of the target shooting will be used to calculate the intraclass correlation coefficient (ICC) and test-retest reliability for this SAR task. The second simulation test is the cognitive function test, which consists of a simple reaction test, a stroop test and a visual search test. Each participant was given at least 2-3 sessions to familiarise him/herself with the cognitive function tests.

#### Experimental procedure

The participants' diets were recorded 3 days prior to the first formal trial and they were asked to repeat the same diet before the next trial. On the day of the experiment, the same breakfast will be served to ensure that the energy intake of the participants is the same.

All experiments were scheduled to start at 8 am. Upon arrival at the assembly site, participants rested in a sitting position for at least 10 minutes. The saliva of the participants was then collected for subsequent biochemical analysis. At the same time. Participants wore a heart rate monitor to record their heart rate and heart rate variability during the experiment. Immediately thereafter, participants chewed either caffeine-containing chewing gum (CAF trail) containing 5 mg/kg or caffeine-free placebo gum (PL trial) for 10 minutes while warming up. After chewing, participants spat out the gum and rested quietly for 15 minutes to collect saliva samples again. Afterwards, a simple reaction test, a stroop test, and a visual search test were performed. At the end of the test, grip strength, reverse action jump and 20-metre sprint were performed under full armour (20 kg load). At the end of the test, the participant was tested on anti-terrorist operations with a Colt 9mm submachine gun. Completion times and target scores were recorded for subsequent analysis. Upon completion of the test, the participant collects another saliva sample to complete the test. The saliva samples are expected to be analysed for  $\alpha$ -Amylase, cortisol and caffeine concentrations.

#### Caffeine and placebo gum

The caffeinated chewing gum used in this study (Military Energy Gum, Arctic Mint flavor; Stay Alert, Chicago, USA) has been used in previous studies (3). Each piece of gum contains 100 mg of caffeine in approximately 5 g of gum. The placebo gum used was a commercially available blue mint gum. In order to provide 4 mg of caffeine per kilogram of body weight and to achieve a double-blind effect, all chewing

gums will be mashed, ground, homogenized, and reshaped with 0.3 g of peppermint flavoring powder, and will be similar in color, appearance, taste, weight, and size. All chewing gums were prepared by specialized personnel and given to the on-site testers after numbering. After chewing the gum, a questionnaire was given to the subjects to confirm whether they could tell the difference between the two chewing gums.

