## **Project summary**

The purpose of this project is to investigate the effects of caffeine chewing gum on the cognitive functions and special operations capabilities of special forces. Using a randomisation crossover design, 20-40 active-duty special forces members who had undergone leave and special forces reserve training were divided into a caffeine trial (CAF) and a placebo trail (PL). After chewing caffeine-containing gum containing 5 mg/kg (CAF group) or caffeine-free gum (PL group) for 15 minutes, we performed a simple reaction test, a stroop test, a visual search test, a grip strength test, a vertical jump test, a 20-metre sprint test, and a counter-terrorism simulation test. A heart rate monitor was used to measure the heart rate and heart rate variability of the participants. Saliva samples were collected and analysed for  $\alpha$ -Amylase, cortisol and caffeine concentrations before the test, after a 15-minute break from chewing gum and at the end of the test. Completion time of cognitive functions, grip strength, vertical jump height, 20 m sprint time, time to completion of the counterterrorism simulation test, and target score will be analysed using paired-sample t-tests.

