## Statistical analysis

All data are presented as averages  $\pm$  standard deviations. The Shapiro–Wilk test was used to examine the normality of the data. The result of were analyzed through a paired sample t test. All data were calculated using SPSS (version 20, Chicago, IL, USA), and the significance level was  $\alpha < 0.05$ .

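### The protocol gives two caffeine doses for its only active treatment: 5 mg/kg in the summary and procedure, 4 mg/kg in the gum-preparation section

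*Protocol*

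**What the plan says.** Three sections of the protocol state the dose of the caffeine (CAF) gum.

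- **Project summary:** "After chewing caffeine-containing gum containing 5 mg/kg (CAF group) or caffeine-free gum (PL group) for 15 minutes".
- **Experimental procedure:** "participants chewed either caffeine-containing chewing gum (CAF trail) containing 5 mg/kg or caffeine-free placebo gum (PL trial) for 10 minutes while warming up".
- **Caffeine and placebo gum:** "In order to provide 4 mg of caffeine per kilogram of body weight", given as a reason for grinding and reshaping the gum, alongside blinding.

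The last section also gives the strength of the commercial product: "Each piece of gum contains 100 mg of caffeine in approximately 5 g of gum". The Design section describes a double-blind crossover with one caffeine trial and one placebo trial, so all three statements concern the same active gum. According to the Statistical analysis section, results are "analyzed through a paired sample t test"; that section does not mention dose.

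**The concern.** Dose defines the only intervention in this trial, and the protocol names two values for it. The figure of 5 mg/kg stands in the text that describes the treatment and the test day. The figure of 4 mg/kg stands in the only text that says how the gum is made up. Staff who prepare gum from the preparation section would make a different dose from the one that the rest of the protocol describes.

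The mismatch might well go unnoticed on site. The gum is prepared and numbered by separate personnel before it reaches the testers, and active and placebo gum are made alike in look, taste and weight.

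Two things are at stake. First, the CAF effect on every outcome, and the salivary caffeine results, could be reported against a dose that was not given. Second, another group could not repeat the trial from this document, because it would not know which dose to prepare.

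**Working it through.** No sample size, power or test statistic is involved, and the protocol shows no derivation of either dose. The check is therefore a direct comparison followed by simple arithmetic.

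**1. Do the statements refer to the same thing?** All three are current protocol text, not a record of earlier changes. The design has one caffeine condition and one placebo condition. There is no second dose level or dose range to which 4 mg/kg could belong.

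**2. Can both figures be true at once?** The summary and procedure speak of what the gum contains, and the preparation section of what it provides. For gum containing 5 mg/kg to provide 4 mg/kg, the fraction released would have to be

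4 / 5 = 80%.

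The protocol states no release or extraction fraction. The 4 mg/kg figure is also given as a reason for making up the gum as described, straight after the caffeine content per piece, so a preparer would naturally convert it directly into an amount of gum.

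**3. Relative size of the gap.**

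- Absolute: 5 − 4 = 1 mg/kg.
- Relative to 5 mg/kg: 1 / 5 = 20%.
- Relative to 4 mg/kg: 1 / 4 = 25%.

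**4. What it means per participant.** Inputs from the section Caffeine and placebo gum: 100 mg of caffeine per piece, about 5 g per piece. Body weight is not given; 60 to 100 kg is an assumption.

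- Caffeine (mg) = dose (mg/kg) × body weight (kg)
- Pieces = caffeine (mg) / 100
- Gum mass (g) = pieces × 5

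| Assumed weight | Caffeine at 5 vs 4 mg/kg | Pieces | Gum mass | Difference |
|---|---|---|---|---|
| 60 kg | 300 vs 240 mg | 3.0 vs 2.4 | 15 vs 12 g | 60 mg, 0.6 piece, 3 g |
| 80 kg | 400 vs 320 mg | 4.0 vs 3.2 | 20 vs 16 g | 80 mg, 0.8 piece, 4 g |
| 100 kg | 500 vs 400 mg | 5.0 vs 4.0 | 25 vs 20 g | 100 mg, 1.0 piece, 5 g |

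The masses leave out the 0.3 g of flavouring powder, which does not alter the comparison.

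**5. Effect on the planned analysis.** The paired t test compares each participant under CAF and under placebo. It uses no dose value, so neither the test nor its significance level changes with the figure chosen.

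**The case against.** The strongest case for a lower grading is that only a label is at risk. No endpoint, test, significance level, sample size or blinding step depends on the figure, and the comparison with placebo is sound if one dose is used throughout. The document also leans one way: 5 mg/kg appears twice, once in the operative procedure, and 4 mg/kg appears once, in a clause of purpose. A drafting slip is a plausible explanation. It may be right, but the documents do not prove it, and the outlying figure sits in the section that governs what is made.

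A second argument is that content and delivered dose need not be equal, since participants spit the gum out after chewing. That is fair in principle, but the protocol neither says that this is meant nor gives the 80% release that it would require.

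Two further points are correct and limit what can be claimed:

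- The preparation section gives an aim but no piece count or weighing rule, so the documents do not show which figure the preparers worked from. A wrong dose is a possibility, not an established fact.
- Salivary caffeine is to be measured at three times, so the concentrations themselves would not be wrong. Only the nominal dose that they are read against could be.

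Finally, the protocol reports an ethics approval number but no approved dose. If the board approved this same text, its approval carries both figures and will not settle the matter.

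None of this removes the contradiction. It narrows the consequence to the identity of the dose.

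**Conclusion.** The concern holds. The protocol states 5 mg/kg in two places and 4 mg/kg in a third for the same single active gum, and offers nothing that reconciles them. The gap of 1 mg/kg (20% of 5, 25% of 4) comes straight from the documents. The per-participant figures of 60 to 100 mg of caffeine, 0.6 to 1.0 piece, or 3 to 5 g of gum rest on an assumed body weight of 60 to 100 kg.

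The validity of the paired comparison is not in question so long as one dose is used throughout. What is uncertain is the dose to which any effect belongs. Because that dose defines the intervention, the correction is required, even though it is small. The documents do not show which figure is right.

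**What to change.** Before any gum is prepared, the sponsor should establish the intended dose, check it against the ethics approval, and state that one mg/kg figure in the Project summary, the Experimental procedure and the section Caffeine and placebo gum. Both the active and the placebo gum should then be sized from it. If the approved text carries both figures, the sponsor must decide between them and tell the board. If a distinction between caffeine contained and caffeine released was intended, the protocol should say so and give the release fraction with its basis.

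If gum has already been made, the report should give the dose actually dispensed, taken from any preparation record.

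The cost is a wording correction in one or two places and a check of the ethics approval and any preparation record. No extra participants, visits or procedures are needed.

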## Statistical analysis

All data are presented as averages  $\pm$  standard deviations. The Shapiro–Wilk test was used to examine the normality of the data. The result of were analyzed through a paired sample t test. All data were calculated using SPSS (version 20, Chicago, IL, USA), and the significance level was  $\alpha < 0.05$ .

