#### Methods

#### Design

This study used a randomization crossover design with a double-blind experiment, divided into a caffeine trial (CAF) and a placebo trail (PL). After the first trial, participants rested for 7-10 days to recover and then proceeded to the next trial, which was expected to be completed within 1 month. During the trial period, all participants maintained their normal training status and there was no change in the training menu.

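### The two-period crossover is analysed with a paired t-test that has no period term, so any shift between trial 1 and trial 2 goes into the error and ties the caffeine estimate to the sequence split

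*Protocol*

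**What the plan says.** The Design section describes a double-blind randomised crossover of a caffeine (CAF) and a placebo (PL) trial: "After the first trial, participants rested for 7-10 days to recover and then proceeded to the next trial". The Participants section expects 20-40 people. The Statistical analysis section states "The result of were analyzed through a paired sample t test". The Project summary lists the outcomes for that test: the cognitive tests, grip strength, jump height and sprint time, ending with "time to completion of the counterterrorism simulation test, and target score will be analysed using paired-sample t-tests". Neither place mentions period or sequence, and the protocol gives no ratio or balancing of the two orders.

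The Pre tests section provides practice before trial 1. For the simulation task, "the participant will undergo at least two anti-terrorist combat simulations to familiarise him/herself with the process of the formal test". For the cognitive tests, "Each participant was given at least 2-3 sessions to familiarise him/herself with the cognitive function tests". Simulation time and score "will be used to calculate the intraclass correlation coefficient (ICC) and test-retest reliability for this SAR task".

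**The concern.** A paired t-test treats all CAF minus PL differences as one sample with a common mean. In a two-period crossover that holds only if nothing changes systematically between the two trials. If performance shifts by *p* from trial 1 to trial 2, the difference carries +*p* for those who take caffeine second and -*p* for those who take it first. The test reads this two-group pattern as noise, although the sequence is known and the pattern can be removed.

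Residual learning is one possible source of *p* for the timed simulation and the cognitive tests. The practice sessions should reduce it. However, no stated rule requires learning to have levelled off before trial 1, and nothing in the analysis depends on the reliability figures. No learning effect is claimed here for grip strength, jump or sprint.

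Two things are at stake: precision in a trial of only 20-40 people, and an estimate that partly reflects how many participants happened to fall into each order.

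**Working it through.** The protocol states no power, effect size or SD, so there is no figure of its own to reproduce.

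**Inputs from the protocol:** two treatments, two periods, 20-40 participants, paired t-test, significance level 0.05 (taken as two-sided).

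**Assumptions:** the period shift *p*, in SDs of the paired difference, from 0 to 1. The true effect is set so that the paired test has 80% power at *p* = 0, which is 0.66 SD at n = 20 and 0.45 SD at n = 40.

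**Model:** d = τ + s·p + e, where d is CAF minus PL, s = +1 if caffeine comes second and -1 if first, and SD(e) = 1. Let n1 participants take caffeine second and n2 take it first.

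- Paired test: mean of all d, n - 1 degrees of freedom. With equal orders the SD it uses is about √(1 + p²·n/(n-1)). At n = 20, p = 0.5: √(1 + 0.25 × 20/19) = √1.263 = 1.12.
- Shift of the paired estimate, given the split: p·(n1 - n2)/n. For 12/8 at p = 0.5: 0.5 × 4/20 = 0.10 SD. For 26/14: 0.5 × 12/40 = 0.15 SD.
- Period-adjusted test: average of the two within-order means, standard error ½·SD·√(1/n1 + 1/n2) with the pooled within-order SD, n - 2 degrees of freedom. The *p* cancels whatever the split.

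Rejection rates come from simulation with 200,000 replicates per setting.

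**Equal orders, n = 20**

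| p (SD) | Paired power | Adjusted power | Paired CI wider by | Paired type I error |
|---|---|---|---|---|
| 0.25 | 78% | 80% | 3% | 4.4% |
| 0.5 | 72% | 80% | 12% | 2.9% |
| 0.75 | 62% | 80% | 26% | 1.5% |
| 1.0 | 49% | 80% | 43% | 0.6% |

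Power at n = 40 is within about one point of these values. With equal orders the paired test is unbiased but conservative.

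**Unequal orders, p = 0.5.** The probability is that of a split at least this uneven under simple randomisation (two-sided binomial).

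| Split | Probability | Shift of estimate | Paired type I error |
|---|---|---|---|
| 12/8 | 50% | 0.10 SD | 4.5% |
| 24/16 | 27% | 0.10 SD | 6.2% |
| 26/14 | 8% | 0.15 SD | 10.7% |

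At 24/16 the paired test has 89% or 50% power depending on which order is larger, against 78% adjusted.

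**Averaged over simple randomisation.** Paired type I error is 4.9-5.1% for every *p* from 0 to 1. At p = 0.5, power is 71% paired against 78% adjusted (n = 20) and 71% against 79% (n = 40). At p = 0.25 it is about 78% for both at n = 20, and 78% against 79% at n = 40. At p = 0 it is 80% against 77.5% (n = 20) and 80% against 79% (n = 40).

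**The case against.** The strongest reply is that the harm depends on a quantity the protocol does not give and tries to keep small. Participants are already trained in counter-terrorism work and practise the tests beforehand. Training is unchanged between trials, and diet, breakfast, start time and seated rest are standardised. The most striking losses need a shift as large as a full SD of the paired difference, and the 80% benchmark is set by this review, not by the protocol. The paired test is also a valid test: unbiased on average, and at its nominal level or below it with equal orders or averaged over simple randomisation. Under simple randomisation it is even slightly the more powerful for small shifts. At n = 20 the two tie at about 0.25 SD; at n = 40 the adjusted test overtakes somewhere between 0.1 and 0.2 SD. The split argument also leans on the protocol's silence about allocation, which may be settled elsewhere.

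Most of this stands as a limit on size. No general rise in false positives can be claimed, and at a shift of 0.25 SD or less the choice makes little difference. It does not remove the point. Practice and standardisation make *p* smaller, but the analysis still has no term for what remains. Nor is the method merely left to an analysis plan, since the protocol names the test in two places. Planned balance would limit the split problem, although unequal dropout could bring it back; with equal orders the loss of power remains.

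**Conclusion.** The concern holds. The protocol fixes an analysis that treats a removable period shift as error and lets the estimate depend on the realised split. With equal orders at n = 20 the cost is about 2 points of power at a shift of 0.25 SD, 7-8 points at 0.5 SD and about 30 points at 1 SD, and none if there is no shift. With unequal orders the estimate moves by p·(n1 - n2)/n, for example 0.10 SD at 12/8 or 24/16 when p = 0.5.

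These sizes rest on assumed values of *p*, an effect set for 80% power, and a two-sided 5% level. The mechanism is algebra and depends on none of them. The change should be made because it is cheap and protects against a plausible shift, not because harm has been shown.

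**What to change.** For the CAF versus PL comparisons listed in the Project summary, replace the paired t-test with a linear mixed model with treatment, period and sequence as fixed effects and participant as a random effect. With complete pairs this is equivalent to a two-sample t-test of the trial 1 minus trial 2 differences between the two orders. The mean difference is τ - p with caffeine first and -τ - p with placebo first, so half the gap between them is τ. Report that period-adjusted difference with its 95% confidence interval instead of the raw mean difference. Use it for all the listed outcomes, since a period shift need not come from learning. Specify it before the treatment codes are opened, and allocate the two orders in equal numbers if this is not already planned.

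This takes one sentence in the Statistical analysis section, and SPSS can fit the model. No new data are needed. The statistical cost is one degree of freedom, plus some efficiency if the orders are unequal. With no period shift, adjusted power is 79.8% at 10/10, 78% at 12/8 and 24/16, and 76% at 26/14, against 80% for the paired test.
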